6.4 PARTICIPANT DISCONTINUATION/WITHDRAWAL FROM THE STUDY

Participants are free to withdraw from participation in the study at any time upon request. An investigator may discontinue or withdraw a participant from the study for the following reasons:

- Pregnancy.
- Significant study intervention non-compliance.
- If any clinical adverse event (AE), laboratory abnormality, or other medical condition or situation occurs such that continued participation in the study would not be in the best interest of the participant.
- Disease progression which requires discontinuation of the study intervention.
- If the participant meets an exclusion criterion (either newly developed or not previously recognized) that precludes further study participation.

- Participants should be withdrawn from study if they start on a new drug or receive antibiotics.

The reason for participant discontinuation or withdrawal from the study will be recorded on a Case Report Form (CRF). Participants who sign the informed consent form but do not receive the study intervention may be replaced. Participants who sign the informed consent form, and receive the study intervention, and subsequently withdraw, or are withdrawn or discontinued from the study, will not be replaced.

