1 PROTOCOL SUMMARY

1.1 SYNOPSIS

Title:	The Effects of an LED Face Mask & Neck and Chest Mask On Skin Health
Study Type:	Single Group, Virtual
Product(s) being tested	The iRESTORE Illumina LED Face Mask and The iRESTORE Illumina LED Neck & Chest Mask
Study Intervention Description:	
This single-group study will involve 38 participants for a total of 12 weeks.
 
Participants will use the test products once daily for 10 minutes in the evening while getting ready for bed.
 
Participants will use Mode 1 only for all sessions of the face mask - the neck and chest mask does not have multiple settings.
 
Participants will complete questionnaires at Baseline, Week 2, Week 4, Week 6, Week 8, Week 10, and Week 12.
 
Participants will also provide photos of their faces at Baseline and Week 12 for dermatologist skin grading.
 
Participants will utilize the test products at home and complete questionnaires online.

Objectives:	
Primary Objective: To examine the effectiveness of the iRESTORE Illumina LED Face Mask and The iRESTORE Illumina LED Neck & Chest Mask in improving skin health outcomes.
 
Secondary Objective: To assess changes in participant perception of skin health.

Endpoints:	
Primary Endpoint: Improvements in skin health parameters will be evaluated by dermatologist grading at Baseline and Week 12.
 
Secondary Endpoint: Participant perceptions of skin health, including plumpness, fine lines and wrinkles, appearance of pigmentation, skin tone and texture, skin redness, firmness, and radiance, and the appearance of crepey skin will be evaluated through subject-specific questionnaires at Baseline, Week 2, Week 4, Week 6, Week 8, Week 10, and Week 12.

Study population	38 female participants aged 25-55
Study Duration:	12 weeks
Description of Sites/Facilities Enrolling Participants:	Virtual

Survey Milestones	Baseline, Week 2, Week 4, Week 6, Week 8, Week 10, and Week 12.
Photo Milestones	Baseline and Week 12

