4.4 END OF STUDY DEFINITION

The study concludes after 12 weeks, with the final collection of data, photos, and participant feedback. Adherence to ethical principles and participant safety is paramount throughout the trial process. Should any significant adverse events arise, the study may be adjusted or halted to prioritize participant well-being.

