6.3 RANDOMIZATION AND BLINDING

There will be no randomization or blinding in this trial.

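### Section 6.4 provides only for leaving the study, with no photo afterwards, so the dermatologist-graded result will in practice rest largely on completers

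*Combined protocol and SAP*

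**What the plan says.** Section 6.4 deals with one kind of event, leaving the study.

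- **Discretionary reasons.** The list opens with "An investigator may discontinue or withdraw a participant from the study for the following reasons". It covers pregnancy, significant non-compliance, and an adverse event or other condition such that "continued participation in the study would not be in the best interest of the participant". It also covers disease progression that requires the intervention to stop, and an exclusion criterion that is newly met or newly discovered.
- **New drug or antibiotics.** The wording here is firmer: "Participants should be withdrawn from study if they start on a new drug or receive antibiotics".
- **What follows withdrawal.** The reason goes on a case report form. Participants who received the devices "and subsequently withdraw, or are withdrawn or discontinued from the study, will not be replaced".

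For the primary endpoint, section 1.1 states: "Improvements in skin health parameters will be evaluated by dermatologist grading at Baseline and Week 12". The Schedule of Activities in 1.3 and the photo instructions in 6.5 give the same two occasions. Section 4.4 describes the end as follows: "The study concludes after 12 weeks, with the final collection of data, photos, and participant feedback". Section 7 promises repeated-measures tests against Baseline. It names no analysis set and no rule for missing data.

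**The concern.** The Week 12 photo is the only post-baseline measurement of the primary endpoint. The two-weekly questionnaires cannot stand in for it, because they measure the secondary endpoint. Someone withdrawn at Week 5, for example, has a Baseline grade and nothing to compare it with, unless a photo is requested that the protocol does not mention.

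This matters if those who leave differ in skin outcome from those who stay. Adverse events, non-compliance and disease progression may all be related to skin grade. So may newly met exclusions: the list in 5.2 includes flare-ups of acne, eczema, rosacea and melasma, cosmetic procedures such as fillers and peels, corticosteroids and retinoids. The primary efficacy result is a mean change from Baseline, so selection into that mean carries straight into the result.

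**Working it through.** **Is there a figure to reproduce?** No. Section 5.4 gives 38 participants without an effect size, SD, error rate, power or expected dropout. The check is therefore a reading of the sections followed by an illustration on assumed values.

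**Reading.**
1. Section 6.4 has no status of being off the devices but still on study. Even a need to stop the intervention appears as a reason to leave the study.
2. Sections 1.1, 1.3, 3 and 6.5 place photos at Baseline and Week 12 only, with no early-termination photo.
3. Section 7 gives no method that would use a Baseline grade without a Week 12 grade.
4. Together, a participant withdrawn before Week 12 ordinarily contributes no primary change score.

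**Size of a possible selection effect (assumed inputs).** Suppose 38 participants receive the devices and w of them have no Week 12 photo for any cause. Let the gap be the completer mean change minus the mean change that those w would have shown had they been photographed, in SD of the change score.

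All-treated mean = [(38 − w) × completer mean + w × lost mean] / 38

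Completer mean − all-treated mean = (w/38) × gap

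| w | w/38 | gap ±0.5 SD | gap ±1.0 SD |
|---|---|---|---|
| 2 | 5.3% | ±0.026 | ±0.053 |
| 4 | 10.5% | ±0.053 | ±0.105 |
| 8 | 21.1% | ±0.105 | ±0.211 |
| 10 | 26.3% | ±0.132 | ±0.263 |

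A positive value means that the completer mean overstates the change. Zero lies inside every range.

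**What a sensitivity analysis would show.** Assume a completer mean of 0.50 SD.
- Missing grades set to no change: 0.50 × 36/38 = 0.474 at w = 2; 0.50 × 28/38 = 0.368 at w = 10.
- Missing grades set to 0.5 SD worse than Baseline: (36 × 0.5 − 2 × 0.5)/38 = 0.447 at w = 2; (28 × 0.5 − 10 × 0.5)/38 = 0.237 at w = 10.

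**Precision, for comparison.** With a two-sided 5% paired t-test and 80% power (also assumed), the detectable change is 0.467 SD with 38 pairs, 0.480 with 36, 0.529 with 30 and 0.560 with 27. The loss of precision is modest, so selection is the larger concern.

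**The case against.** The strongest reply is that a grade taken after a new drug cannot be attributed to the devices. Section 5.1 asks for stable products and routines, and section 6.3 confirms the open design: "There will be no randomization or blinding in this trial". Leaving such grades out is a defensible choice. That stands as an argument about which analysis should be primary. It does not argue against collecting the photo, because a collected grade can be excluded later and an uncollected one cannot be recovered.

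Other replies stand in part:

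- **Discretion.** Most reasons only permit withdrawal, so how often it will happen is unknown. Only the new-drug wording is firmer, and that is the group for which the direction of bias is least clear.
- **Cause of loss.** Participants may also leave by choice or simply not respond. Only part of w is due to 6.4, and only part could be recovered.
- **Other documents.** The consent form mentioned in 8.1 and the Manual of Procedures mentioned in 8.5 were not available for this review and might cover data after withdrawal.

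Two stronger readings are tempting. A reader might infer that the protocol prescribes a completer analysis or bars a later photo. It does neither, and reliance on completers is the practical consequence of what it leaves out. A reader might also infer that the selection must flatter the devices. That is plausible for withdrawals due to adverse events or non-compliance, but nothing in the documents establishes it, and someone starting a new drug could have done better or worse than completers.

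**Conclusion.** The point holds as a matter of design. Followed as written, the plan ordinarily loses the only post-baseline primary measurement for anyone withdrawn, and the graded result will in practice rest largely on completers. The bias is of unknown size and its direction is not established. On assumed all-cause losses of 2 to 10 of 38 and a gap of up to 1 SD, it is at most 0.05 to 0.26 SD either way. These figures show sensitivity to assumptions; they do not demonstrate a bias. The change is worth making because it is cheap and protects primary data, not because the result is already known to be wrong.

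One ambiguity in 6.4 adds to this. Starting a drug listed in 5.2 falls under the discretionary wording for a newly developed exclusion and also under the firmer new-drug wording. The passages must be reconciled; this review does not choose the rule.

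**What to change.** 1. Leave unchanged the decisions on stopping the devices and on withdrawal in the participant's interest, but separate stopping the devices from leaving the study.
2. Where the participant still consents, and the investigator does not judge remote follow-up to be against her interest, still request the Week 12 photo and the remaining questionnaires.
3. Report the graded change for all who received the devices and had a Week 12 photo, beside an analysis that excludes grades taken after a new drug. Fix which of the two is primary before Week 12 photos are graded.
4. Add a sensitivity analysis that sets missing Week 12 grades to no change, and then to a less favourable value stated on the grading scale used.
5. Report withdrawals by reason, which the case report form already captures.
6. Reconcile the two wordings in 6.4 that apply to a newly started drug listed in 5.2.

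The cost is protocol wording, a short analysis text and a few reminders, since participation is already remote: "Participants will utilize the test products at home and complete questionnaires online". Participants also take the photos themselves. The estimate may become smaller or larger. Grades taken after a new drug may include that drug's effect, which is why the analysis without them is reported alongside.

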6.5 PHOTO INSTRUCTIONS

Photographs will be taken at Baseline and Week 12 to document changes in appearance.

Face guidelines:

- You will be required to provide photos taken straight on, directly facing the camera, and from the sides at each measurement time point.
- Hair should be tied back.
- The photo should include your full face/head only, with no more than the top of your shoulders visible.
- No cropping: your full face, head, and ears should be included.
- Please use natural light, in a direction that your phone does not cast a shadow on your face when taking the photo, without using the flash.
- Do not use any type of camera filter setting. No makeup should be worn. Neutral facial expression.
- If possible, take your photos in the same location, at the same time of day, and in the same lighting at each check-in.

Neck and Chest Guidelines:

- The photo should be taken straight ahead.
- Please use natural light, in a direction that your phone does not cast a shadow on your face when taking the photo, without using the flash.
- Do not use any type of filter setting. No makeup should be worn. Neutral facial expression.
- If possible, take your photos in the same location, at the same time of day, and in the same lighting at each check-in.

6.6 REQUIRED DEVICES

Smartphone or digital camera to be provided by participants. iRESTORE Illumina LED Face Mask and The iRESTORE Illumina LED Neck & Chest Mask will be provided by the sponsor.

7 STATISTICAL CONSIDERATIONS

Following data collection and the completion of the trial, the data will be analyzed by Citruslabs to determine the effect of the intervention. Repeated-measure, between time points, statistical tests will be used to examine changes in primary and secondary endpoints versus the Baseline.

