3 OBJECTIVES AND ENDPOINTS

OBJECTIVES	ENDPOINTS	TIMEPOINTS	ASSESSED BY	JUSTIFICATION FOR ENDPOINTS
Primary Objective : To evaluate changes in overall skin appearance, as measured by dermatologist skin grading.	Improvement in Skin Appearance	Baseline and Week 12	Photographs via Dermatologist Skin Grading	Standardized photographs provide objective data on the changes in skin appearance, specifically targeting wrinkles, fine lines, and other signs of aging.

Secondary Objectives: To assess changes in a range of skin health parameters.	Improvement in skin plumpness, fine lines and wrinkles, pigmentation, tone and texture, redness, firmness, elasticity, radiance, and appearance of crepey skin.	Baseline, Week 2, Week 4, Week 6, Week 8, Week 12	Questionnaires	Self-reported questionnaires provide subjective data on perceived changes in wrinkles and fine lines.
--	---	---	----------------	---

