4 STUDY DESIGN

4.1 OVERALL DESIGN

This 12-week single-group, virtual clinical study is designed to evaluate the efficacy of the iRESTORE Illumina LED Face Mask and The iRESTORE Illumina LED Neck & Chest Mask. The study will involve 38 participants, aged between 25 and 55 years, with self-reported skin issues, who will use the devices once daily for 10 minutes daily for 12 weeks.

Data collection will include questionnaires at Baseline, Week 2, Week 4, Week 6, Week 8, Week 10, and Week 12. In addition, participants will provide photos at Baseline and Week 12 to assess changes in skin health and appearance.

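### Section 7 tests the questionnaire endpoints against Baseline with no key time point, attribute ranking or error control; read naturally, that is 40 to 54 unadjusted secondary tests

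*Combined protocol and SAP*

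**What the plan says.** Section 7 has two sentences. The first says who analyses the data. The second is the whole method: "Repeated-measure, between time points, statistical tests will be used to examine changes in primary and secondary endpoints versus the Baseline". It names no test or model, significance level, sidedness, key visit, order of endpoints or adjustment for multiple tests, and no other section supplies them.

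The secondary endpoint is described in two places that differ:

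- Section 1.1 (synopsis) lists 8 attributes: "plumpness, fine lines and wrinkles, appearance of pigmentation, skin tone and texture, skin redness, firmness, and radiance, and the appearance of crepey skin".
- Section 3 lists 9, adding elasticity: "Improvement in skin plumpness, fine lines and wrinkles, pigmentation, tone and texture, redness, firmness, elasticity, radiance, and appearance of crepey skin".
- Section 3 gives the questionnaire times as "Baseline, Week 2, Week 4, Week 6, Week 8, Week 12", which is 5 follow-ups.
- Section 4.1 gives 6: "Data collection will include questionnaires at Baseline, Week 2, Week 4, Week 6, Week 8, Week 10, and Week 12". The synopsis, Section 1.2 and Section 6.1 agree with Section 4.1.

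The primary endpoint has one follow-up: "Improvements in skin health parameters will be evaluated by dermatologist grading at Baseline and Week 12". The repeated looks over time therefore fall on the questionnaire. Section 5.4 justifies the 38 participants partly by the prospect of statistically significant results, so significance testing is intended.

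**The concern.** A rule that compares endpoints with Baseline between time points, applied to an endpoint made of 8 or 9 attributes, leads an analyst to a grid of attribute-by-visit tests. Nothing in the plan says which cell of the grid carries the conclusion. A single attribute that crosses the threshold at Week 2 could be reported as a significant improvement with the same formal standing as one at Week 12, although Section 4.2 justifies the design by its 12-week length.

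At stake is whether a reported secondary improvement can be told apart from the best of several dozen looks. Reconciling the two attribute lists and visit schedules would not cure this, because one agreed list still leaves a grid of similar size with no error control.

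**Working it through.** **Inputs from the documents.** Attributes: 8 (Section 1.1) or 9 (Section 3), counting compound items such as fine lines and wrinkles once. Follow-ups: 5 (Section 3) or 6 (Sections 1.1, 1.2, 4.1, 6.1). Participants: 38, in a single group. The documents give no error rate or test count to reproduce, and no inputs from which 38 could be derived.

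**Assumptions.** Two-sided 5% per test, so 2.5% in the improvement direction. No true change in any attribute. Correlations are not given, so a range is used.

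**Step 1: number of tests, attributes × follow-ups.** 8 × 5 = 40; 9 × 5 = 45; 8 × 6 = 48; 9 × 6 = 54. Splitting the two compound items in the Section 3 list gives 11 × 5 = 55 or 11 × 6 = 66.

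**Step 2: independent tests.** P(at least one false improvement) = 1 − 0.975^k. P(at least one p < 0.05 in either direction) = 1 − 0.95^k.

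| k | False improvement | Either direction |
|---|---|---|
| 40 | 63.7% | 87.1% |
| 45 | 68.0% | 90.1% |
| 48 | 70.3% | 91.5% |
| 54 | 74.5% | 93.7% |

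The last column also counts false worsening, so it is not the rate of false claims of benefit.

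**Step 3: correlated tests.** Independence cannot hold here: every visit is compared with the same Baseline, and the same women rate overlapping attributes. A null simulation used n = 38, paired t-tests against a shared Baseline, correlation 0.5 between visits, and 4,000 runs per setting. P(at least one false improvement):

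| Between-attribute correlation | 45 tests | 48 tests | 54 tests |
|---|---|---|---|
| 0 | 58.9% | 59.1% | 61.7% |
| 0.3 | 47.2% | 47.9% | 50.7% |
| 0.5 | 39.4% | 40.5% | 42.8% |
| 0.7 | 31.2% | 32.4% | 34.4% |
| 0.9 | 18.9% | 22.6% | 22.8% |

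For correlations from 0.3 to 0.9 the rate is about 20% to 50%. At the lower end that is about eight times the single-test rate (20 / 2.5 = 8), and at the upper end about twenty times (50 / 2.5 = 20).

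**Step 4: what the remedy achieves.** Restricting to Week 12 without adjustment is not enough. With 9 independent attributes, 1 − 0.975^9 = 20.4% for a false improvement; the simulation gives about 6% to 18% for correlations 0.9 to 0.3. Holm's first threshold with 9 attributes is 0.05 / 9 = 0.0056. When nothing changes, Holm makes an error only if some attribute passes that threshold. The simulated rate is then about 2% to 5% in either direction, and about 1% to 3% for a false improvement. The second figure is the one to set against the table in Step 3.

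**Step 5: price in power.** Take a paired t-test with 38 pairs (37 degrees of freedom) and 80% power. Solving the noncentral t for the mean change, in units of the SD of the changes, gives 0.467 SD at 0.05 and 0.619 SD at 0.0056.

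**The case against.** Several objections have force.

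- **The grid is inferred.** Section 7 does not say that every attribute is tested at every visit. An omnibus repeated-measures test for each attribute, or a scored questionnaire, would also fit its words. A reader might infer that the plan prescribes about 50 tests; the text does not go that far. What stands is that the grid is the natural reading and nothing in the plan rules it out.
- **A false improvement is not shown to be likely.** A reader might take the 64% to 75%, or the 87% to 94%, as the expected rate. The first range needs independent tests, which a shared Baseline excludes; the second also needs independence and counts worsening too. With correlated answers the rate is mostly below one half.
- **No threshold is written.** The 5% is an assumption, so every rate above depends on it.
- **Week 12 has some standing.** Section 4.2 treats 12 weeks as long enough to judge effectiveness. That is a rationale for duration, not a rule about which comparison counts.
- **These are secondary self-ratings.** The primary endpoint has only Week 12, so its result is not one of many looks over time. Labelling all questionnaire results exploratory and giving intervals would also answer the concern, at the cost of any confirmatory secondary claim.
- **Adjustment does not supply a control.** A reader might infer that a Holm-adjusted result shows that the devices work. It would not: the study has a single group, and Section 6.3 says there is no randomization or blinding.

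**Conclusion.** The concern holds in this form. Section 7 leaves the questionnaire endpoints without a key time point, an attribute ranking or error control, and its natural reading gives 40 to 54 secondary tests. If nothing changes, the chance of at least one false improvement is about 20% to 50% with correlated answers and 64% to 75% under independence, against 2.5% for one test.

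This rests on a two-sided 5% level that the documents do not state, on visit-by-visit testing of each attribute, and on assumed correlations (0.3 to 0.9 between attributes, 0.5 between visits). The lack of control is firmly established; its exact size is not. It should be put right before analysis, but it affects secondary outcomes only and does not undermine the single-time-point primary comparison.

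**What to change.** First reconcile the test family: decide whether elasticity is an attribute and whether Week 10 is a questionnaire visit, and make Sections 1.1 and 3 agree. Then add to Section 7, in substance:

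> For the questionnaire, Week 12 versus Baseline is the key comparison. The listed attributes will be tested at Week 12 with Holm's procedure at an overall two-sided 5% level. Results at all earlier visits will be reported as mean changes with 95% confidence intervals, without claims of significance.

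The paired test to be used should be named in the same paragraph. A composite of all attributes tested before the single ones is optional, and only sensible if every item shares one scale and direction; the documents give no item scales, so this cannot be judged from them.

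The cost is a few sentences, with no new data or visits. The downside is power for single attributes: with 9 attributes and 38 complete pairs, the first Holm step needs a change of about 0.62 SD for 80% power, against 0.47 SD unadjusted. Missing Week 12 questionnaires would raise both figures, and Section 6.4 does not replace participants who withdraw after receiving the devices.
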